# Activities

[figure not shown]
# 2.3 Project Activities and Output

S/No	ACTIVITIES	KPI	DURATION
			(Months)
1.	Facility upgrade  • Procurements	
 
All Secretarial Materials:         
 
Stationaries
 
Analytical soft ware
 
Laptop
 
 
 
Chemicals and Reagents
 
Equipment (Spray dryer, HPLC,) are available and in store
 
Collection of Plant Biomass, Excipients.
 
	5
2.	Optimization of Processes	Validated New Optimized Processes for: Extraction and Concentration available: SOPs and Protocols available. Prepared according to ISO 17025 and cGMP Standard.	3
3.	Pilot Commercial Extraction of NIPRIMUNE herbal active ingredient.	At least 100 kg of NIPRIMUNE Herbal extract available in store.	4
4.	Quality Control of NIPRIMUNE herbal active ingredient.	Data on the QC of the different batches of NIPRIMUNE herbal active ingredient available.	5
7.	Pilot Commercial Production of NIPRIMUNE Capsules	At least 10 batches of NIPRIMUNE capsules (Each batch 100 x 30 capsules Batches for Clinical Trial produced NIPRIMUNE Batches for commercial distribution available.  In process QC record available Effective QC data available.	6
8.	Shelf life Stability testing of NIPRIMUNE	Data on shelf life available. Expiry date of batches available.	6
9	Distribution to pharmacies	

List of Distributors available

Record of sales

	6
10	Develop of clinical trial protocol.	Soft and hard copies of Clinical Trial Protocols all available	2

1			
Obtain	Ethical Approval	Approval from:  • National Health Research Ethics Committee (NHREC).	2
Select	ion of volunteers	
 
25 Healthy adult volunteers selected using the selection guideline.
 
Informed written consent of each volunteer available.
 
	1
Evaluat	tion of Medical of all volunteers	Demographic and Baseline Characteristics examination result available:  i. Sex ii. Weight, height iii. Vital signs: Blood pressure, pulse, and temperature iv. Complete hematology: WBC, differential, HCT, Hgb, platelets v. Body Mass Index (BMI) vi. Blood chemistry (Na, K, Cl, CO2, BUN, Creatinine, albumin, alkaline phosphatase, LDH, ALT, AST, bilirubin total and direct, glucose, cholesterol, triglycerides, Serum pregnancy Test vii. Urinalysis (pH, gram stain, color, glucose, cells, protein, specific gravity).	2
placebo with m	nized, single-blind, o-controlled study ultiple ascending	Data available on each volunteer:  Data available:  • Pharmacokinetics (PK) (	5
dosing	of volunteers.	Absorption, distribution, metabolism, and excretion (ADME) of NIPRIMUNE.	

	
 
Data on Maximum Tolerated Dose (MTD)
 
Pharmacodynamics (PD): The general effect of NIPRIMUNE on the body.
 
Immunogenicity: Evaluating the immune response to NIPRIMUNE.
 
	
Data Collection and analysis	Processed data available and are adequately stored.	10
Report writhing	Report for all activities compiled	11

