#### Introduction

This is a Phase I clinical study of NIPRIMUNE, the Investigational Medicinal Product (IMP). The current study is designed to evaluate the safety and tolerability and pharmacokinetics of single and multiple oral doses of the IMP NIPRIMUNE, in healthy volunteers.

This phase 1 clinical trial is being undertaken to determine the safety of NIPRIMUNE in healthy human participants. Physical well-being, including laboratory investigations, will be closely monitored and evaluated. The clinical trial will be carried out in NIPRD Research Clinic and other accredited laboratory. The use of appropriate health diary by the patients will be introduced in the study.

NIPRIMUNE is a phyto-medicine that has demonstrated positive outcomes during in vitro and in vivo studies with anti-inflammatory ,antiviral and strong immunomodulatory characteristics.

This clinical study is planned as a double blind, randomised, placebo-controlled, combined clinical study of two parts: Single Ascending Dose (SAD) and Multiple Ascending Dose (MAD) studies, respectively. Pharmacokinetic (PK) profile of the NIPRIMUNE, will also be assessed in both parts of the study. The safety, tolerability and pharmacokinetic data and results obtained from this study will determine the potentially efficacious doses of the IMP NIPRIMUNE in the subsequent efficacy studies.

Between each cohort, an interim analysis of PK, safety and tolerability will be performed. The available data will be evaluated by an independent Drug Safety Monitoring Board (DSMB). Once a dose level is judged to be safe, the DSMB will allow the escalation to the next cohort.

Both the Investigator and study participants will remain blinded to the treatment administered (drug or placebo) till the final results of the study are obtained.

DSMB will provide recommendations about stopping, modifying or continuing the study. Decision to escalate to next dose level/ Cohort, will be based on interim analysis of pharmacokinetic data, 36-hr post-dose, and 30-days post dose safety follow-up.

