## Study Site: NIPRD Research Clinic IDU

**Study Population:** Fifty six healthy participants will recruited from our pool of clients and from the eleven communities located around the institute.

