## **Study Design**

**Interventional Model Description:** Phase I, Randomized, Double-blind, Placebo-controlled, Single Ascending Dose and Multiple Ascending Dose Clinical Study to Assess the Safety, Tolerability and Pharmacokinetics of the Investigational Product in Healthy Adult Volunteers

Both the Investigator and study participants will remain blinded to the treatment administered (drug or placebo) till the final results of the study are obtained.

The placebo will identical to the investigational medicinal product in smell, taste, and appearance.

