#### **Arms and Interventions**

Participant Group/Arm	Intervention/Treatment
Experimental: NIPRIMUNE is a phytomedicine that has demonstrated positive outcomes during in vitro and in vivo studies for immune	NIPRIMUNE is a small molecule with demonstrated antiviral and immunomodulatory activity in-vitro & in

Participant Group/Arm	Intervention/Treatment
booster with antiviral charactreristics	vivo studies., it was anticipated that NIPRIMUNE can also be a promising immune booster
Formulated as Capsules intended for oral dosing to trial participants.	
Placebo Comparator: Placebo  placebo will be identical in smell, taste, and appearance to the Capsule of NIPRIMUNE	Placebo capsules identical in appearance, taste and smell to the capsules of NIPRIMUNE

This clinical study is planned as a double blind, randomised, placebo-controlled, combined clinical study of two parts: Single Ascending Dose (SAD) and Multiple Ascending Dose (MAD) studies, respectively. Pharmacokinetic (PK) profile of the NIPRIMUNE, will also be assessed in both parts of the study. The safety, tolerability and pharmacokinetic data and results obtained from this study will determine the potentially efficacious doses of the IMP NIPRIMUNE, in the subsequent efficacy studies.

Fifty six (56) healthy volunteers will be recruited age for sex. Randomised, The SAD Part will consist of 5 cohorts of 8 healthy adult volunteers, each volunteer will be randomly (blinded) allocated to NIPRIMUNE or placebo (each cohort will consist of 6 volunteers receiving NIPRIMUNE and 2 volunteers receiving placebo). Five (5) dose level of the investigational medicinal product are selected for oral administration. The MAD Part will consist of 2 cohorts of 8 healthy adult volunteers, each volunteer will be randomly (blinded) allocated to NIPRIMUNE or placebo (each cohort will consist of 6 volunteers receiving NIPRIMUNE and 2 volunteers receiving placebo). Two (2) dose levels of the investigational medicinal product are selected for oral administration. Additional Volunteers will be enrolled to replace(volunteers withdrawing consent from the study for reasons other than safety). Additional volunteers will also be enrolled if a Cohort needs to be repeated.

Safety evaluation during both the SAD & MAD pars of the clinical study will include adverse events, clinical laboratory/ pathological test results, electrocardiogram (ECG), and measurement of vital signs.

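### The activities table plans 25 volunteers and a single-blind study, while the clinical section plans 56 and double-blind; its 5-month slot and missing single-dose part also need reconciling

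*Protocol*

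**What the plan says.** The clinical section is consistent on size and blinding. Under Study Population: "Fifty six healthy participants will recruited from our pool of clients". Under Arms and Interventions: "Fifty six (56) healthy volunteers will be recruited age for sex", built up as "The SAD Part will consist of 5 cohorts of 8 healthy adult volunteers" and "The MAD Part will consist of 2 cohorts of 8 healthy adult volunteers", each cohort with 6 on active treatment and 2 on placebo. The trial title, Introduction, Study Design and Arms and Interventions all call the study double-blind. Study Design adds "Both the Investigator and study participants will remain blinded to the treatment administered (drug or placebo", and says that this holds until the final results are available.

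On escalation, the Introduction calls for an interim analysis between cohorts and bases the decision on pharmacokinetic data, "36-hr post-dose, and 30-days post dose safety follow-up". Study Procedure and the primary outcome statement follow participants for 12 weeks.

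The table in section 2.3 Project Activities and Output differs. Its selection row reads "25 Healthy adult volunteers selected using the selection guideline". Its conduct row, broken across table cells, reads "single-blind, o-controlled study ultiple ascending" and continues with the dosing of volunteers. The duration column, headed in months, shows 5 for that row. No row names a single-ascending-dose activity.

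**The concern.** One current document gives two sample sizes and two levels of blinding for the same trial. The table holds the performance indicators against which delivery is measured, so a team could meet its selection target and still leave most cohorts unfilled.

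Blinding matters because part of the primary safety assessment rests on judgement. The primary outcome statement uses adverse-event severity, and the outcome table classifies serious adverse events by relation to the product. An assessor who knows the allocation may grade either differently. With only 2 placebo recipients per cohort, a few shifted judgements could change the comparison.

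Two further differences are less certain. The conduct row leaves out the single-dose part, which holds 40 of the 56 volunteers. The 5-month slot looks short for seven cohorts separated by 30-day reviews.

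**Working it through.** **Sample size.** Inputs are from Arms and Interventions.

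- Total: 5 × 8 + 2 × 8 = 40 + 16 = 56. The stated figure reproduces.
- Active: 7 × 6 = 42. Placebo: 7 × 2 = 14.
- Table target: 25 / 56 = 45%. 25 / 8 = 3 cohorts, remainder 1, which gives 3 × 6 = 18 active and leaves 4 of 7 cohorts empty.
- Could 25 refer to one part only? The single-dose part needs 40 and the multiple-dose part 16, so it matches neither.

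**Blinding.** The title, Introduction, Study Design and Arms and Interventions say double-blind. The conduct row in section 2.3 says single-blind. The word is intact although the row is split. The row does not say who would be unblinded.

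**Study parts.** The conduct row names multiple ascending dosing only, and no other row covers single dosing. This is an omission, not a statement that single dosing is dropped.

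**Duration.** Inputs: 30 days after the last dose before the next cohort (Introduction); 7 dosing days in the multiple-dose part, so the last dose falls 6 days after the first; 12 weeks = 84 days of follow-up from first dose; 30.44 days per month. Day 0 is the first dose of the first cohort. DSMB time, bioanalysis, screening and repeated cohorts are set to zero, which favours the table. The table's slot is 5 × 30.44 = about 152 days.

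Cohorts in sequence:

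- Single-dose cohorts start on days 0, 30, 60, 90 and 120. The last review closes on 120 + 30 = day 150.
- First multiple-dose cohort: first dose day 150, last dose day 156, review closes on day 186.
- Second multiple-dose cohort: first dose day 186, last dose day 192.
- Its 30-day follow-up ends on 192 + 30 = day 222 (7.3 months).
- Its 12-week follow-up ends on 186 + 84 = day 270 (8.9 months).

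Other arrangements of the two parts (assumptions, not described in the protocol):

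| Arrangement | 30-day follow-up complete | 12-week follow-up complete |
|---|---|---|
| In sequence | day 222 (7.3 months) | day 270 (8.9 months) |
| Multiple-dose part starts after the third single-dose review (day 90) | 90 + 36 + 36 = day 162 (5.3 months) | 90 + 36 + 84 = day 210 (6.9 months) |
| Wholly in parallel from day 0 | 120 + 30 = day 150 (4.9 months) | 120 + 84 = day 204 (6.7 months) |

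Only the wholly parallel case, without the 12-week visits, fits within 152 days.

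**The case against.** The best defence is that section 2.3 is a project-management table. The clinical section governs conduct and is consistent on 56 volunteers and double-blinding, so staff would probably follow it. That limits the likely harm but does not remove the contradictions.

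Several stronger readings are tempting, and the documents do not support them:

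- **The escalation rule alone makes 5 months impossible.** It does not. With the two parts wholly in parallel and no DSMB time, every 30-day window closes by day 150. No escalation follows the last cohort either, so its own window is not an escalation constraint.
- **The row must contain all follow-up.** This is uncertain. Data collection and analysis has its own row marked 10 and report writing one marked 11. Those values also raise doubt about how the column was filled in, although its header says durations in months. The activities figure is not in the text at hand and may show the sequence.
- **The one-month pre-dose diary should be added to the 5 months.** Selection (1 month) and medical evaluation (2 months) are separate, earlier rows and could hold it.
- **The single-dose part has been abandoned.** The row is a broken, shortened label. It omits that part without excluding it.
- **The 12-month project claim is shown to fail.** It is not, because the overlap between rows is not stated.
- **All primary outcomes depend on unblinded judgement.** Most rows of the outcome table are event counts, discontinuations or marked-abnormality criteria. Severity and relatedness are the exposed elements.

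**Conclusion.** The contradictions on sample size (25 against 56) and blinding (single against double) are established and need no assumption. At 25, 18 volunteers receive active treatment instead of 42, and 4 of 7 cohorts cannot be filled. The bias from single-blind conduct depends on the investigator being the unblinded party, which the table does not state.

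The missing single-dose part is a probable drafting omission.

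The duration conflict is conditional. Five months do not hold seven sequential cohorts: the last cohort's first dose already falls on day 186. They also do not hold the 12-week follow-up under any arrangement examined (day 204 at the earliest), if that follow-up belongs to the row. Sequence is the natural reading, since the Introduction places an interim analysis between cohorts and describes no overlap of the two parts. It remains an assumption for the multiple-dose part relative to the single-dose part.

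**What to change.** In section 2.3, correct the selection row to 56 volunteers (40 single-dose, 16 multiple-dose). Correct the conduct row to double-blind and name both ascending-dose parts.

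For timing, the sponsor and the DSMB should reconcile three things before the first cohort: the 5-month duration, the between-cohort review in the Introduction, and the 12-week follow-up. This should not presume which passage is right. The protocol should then state whether the two parts overlap and which row holds the follow-up visits. The 12-month completion claim in the Executive Summary should be checked at the same time.

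The sample-size, blinding and study-part corrections change table wording only and leave the design in the clinical section as it is. The timing item costs a short joint review and may lead to a different stated duration.

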## Gant chart of activities and key performance indicators

#### **Milestones and Deliverables**

- o cGMP-Compliant Facility: A facility that meets international quality standards for industrial-scale production of NIPRIMUNE.
- o Standardized NIPRIMUNE Granules: NIPRIMUNE granules that meet international quality standards.
- o Phase 1 Clinical Trial Report: A report on the safety, tolerability and immunomodulatory activity of NIPRIMUNE in healthy volunteers.
- o Commercialization Plan: Commercial distribution of NIPRIMUNE.

